2.1 ANALYSIS ENDPOINTS

2.1.1 Demographic and baseline characteristics

The baseline value is defined as the last available value prior to the first dose of study medication, SC IMP.

All baseline safety and efficacy parameters (apart from those listed below) are presented along with the on-treatment summary statistics in the efficacy and safety sections ([Section 2.4.4](#) and [Section 2.4.5](#)).

Demographic characteristics

The following demographic characteristics will be summarized separately by treatment and overall:

- Sex (Male, Female)
- Race (Caucasian/White, Black, Asian/Oriental, Other)
- Ethnicity (Hispanic, Not Hispanic)
- Region (Region 1 [Western countries], Region 2 [South America], and Region 3 [Rest of the World]); definitions of the regions are provided in [Section 2.5.7](#)
- Age (years)
- Age group (≥ 50 and < 65 , ≥ 65 and < 75 , ≥ 75 and < 85 , ≥ 85 years)
- Weight (kg)
- Weight group (< 60 , ≥ 60 and < 100 , ≥ 100 kg)
- Body mass index (BMI, kg/m^2)
- BMI group (< 25 , ≥ 25 and < 30 , ≥ 30 kg/m^2)
- Smoking status (never, former, current)
- Alcohol habits (never, occasional, monthly, weekly, daily)

Medical or surgical history

Medical or surgical history includes all the relevant findings within the lifetime of the patient.

This information will be coded to a “Lower Level Term (LLT)”, “Preferred Term (PT)”, “High Level Term (HLT)”, “High Level Group Term (HLGT)”, and associated primary “System Organ Class (SOC)” using the version of Medical Dictionary for Regulatory Activities (MedDRA) currently in effect at Sanofi at the time of database lock.

Disease characteristics at baseline

The following baseline disease characteristics as well as the other baseline characteristics will be summarized separately by treatment group:

- Unequivocal cranial symptoms of GCA (Yes, No)
- Unequivocal symptoms of PMR (Yes, No)
- Other features judged by the investigator to be consistent with GCA or PMR flares (Yes, No)
- Diagnostic temporal artery biopsy (Yes, No)
- Diagnostic imaging performed (Yes, No) and imaging methodology (Angiography, CTA, MRA, PET-CT, Ultrasound)
- Duration of GCA (from diagnosis date to baseline)
- GCA Disease onset (new onset, refractory)
- Prior GCA flares (≤ 6 months, 6 to 12 months or >12 months prior to screening)
- Prednisone dose at baseline
- Prednisone dose group at baseline (≤ 30 mg/day, >30 mg/day)
- Highest dose and duration of corticosteroid taper taken for GCA within 24 weeks prior to screening
- Physician global assessment of disease activity (MD-VAS)
- C-reactive protein (CRP) at baseline
- CRP group (\leq median, $>$ median)
- ESR at baseline
- ESR group (\leq median, $>$ median)
- $ESR \geq 30$ mm/h and/or $CRP \geq 10$ mg within 6 weeks prior to screening (Yes, No)
- Glucocorticoid toxicity at baseline*

*The baseline glucocorticoid toxicity is established by a composite index calculated from weighted scores assigned by toxicities. The scores are described in [Appendix I](#).

Any technical details related to computation, dates, and imputations for missing dates are described in [Section 2.5](#).

2.1.2 Prior or concomitant medications

All medications taken within a certain period of time before randomization and until the end of the study, including vaccines taken before screening, biological/non-biological disease modifying anti-rheumatic drugs [DMARDs] and immunosuppressive agents taken for patients with symptomatic GCA disease are to be reported in the case report form (CRF) pages. The highest dose and duration of all corticosteroids taper taken for GCA within the 24 weeks prior to screening and all corticosteroids taken during the study are also reported.

All medications will be coded using the World Health Organization – Drug Dictionary (WHO-DD) version currently in effect at Sanofi at the time of database lock.

- Prior medications are those the patient used prior to first investigational medicinal product (IMP) intake. Prior medications can be discontinued before first dosing or can be ongoing during treatment phase.
- Concomitant medications are any treatments received by the patient concomitantly to the IMP, during the treatment-emergent period ([Section 2.1.3](#)).

A given medication can be classified as a prior medication, as a concomitant medication, and/or as a post-treatment medication.

For patients who experience a disease flare and are in need of rescue therapy, study patients prescribed with rescue corticosteroids (non-investigational medicinal product) per investigator judgement during the course of the study will continue administration of subcutaneous (SC) IMP (sarilumab or its matching placebo) for the full duration of the 52-week treatment period.

Any technical details related to computation, dates, imputation for missing dates are described in [Section 2.5](#).

2.1.3 Efficacy endpoints

2.1.3.1 Primary efficacy endpoint(s)

The primary endpoint is the proportion of patients achieving sustained remission at Week 52, where the sustained remission at Week 52 is defined as having met all following parameters:

1. Achievement of disease remission not later than Week 12,
2. Absence of disease flare from Week 12 through Week 52,
3. Normalization of CRP (to <10 mg/L, with an absence of successive elevations to ≥ 10 mg/L) from Week 12 through Week 52, and
4. Successful adherence to the prednisone taper from Week 12 through Week 52.

Based on patients' enrollment dates and the study discontinuation plan, not all the patients had an opportunity to complete the 52-week treatment period. For the cohort of patients who did not have an opportunity to complete the 52-week treatment period, it is not meaningful to define the endpoint of sustained remission at Week 52. Therefore, the analysis of primary endpoint will be

limited to the cohort of patients who had an opportunity to complete the 52-week treatment period. The detail definition of this cohort can be found in [Section 2.3.1](#).

Components of primary endpoint are described as below:

1. Achievement of disease remission not later than Week 12

Disease remission is defined as resolution of signs and symptoms of GCA, and normalization of CRP (<10 mg/L). Note that a single CRP elevation (≥ 10 mg/L) is not considered absence of remission unless CRP remained elevated (≥ 10 mg/L) at the next study visit.

The status of normalization of CRP (<10 mg/L) will be determined based on the last two non-missing post-baseline CRP values measured up to Week 12. If at least one of them is <10 mg/L, then it is considered as normalization of CRP.

Signs and symptoms of disease

Evaluation of clinical signs and symptoms by the Efficacy Assessor at every study visit according to the schedule of assessment will include the following:

- Symptoms of PMR as indicated by the Efficacy Assessor (morning stiffness and/or pain, in the shoulder and/or hip girdles)
- Cranial symptoms.
 - Localized headache.
 - Temporal artery or scalp tenderness.
 - Visual signs or symptoms such as acute or subacute vision loss due to arteritic anterior ischemic optic neuropathy (A-AION), transient blurry vision (generally monocular or at least affecting 1 eye at a time, but potentially affecting both eyes), diplopia.
 - Jaw or mouth pain, tongue claudication.
- Constitutional syndrome, including but not limited to fever, malaise, unintentional weight loss, night sweat, asthenia, fatigue, loss of appetite.
- New or worsened extremity claudication, bruits and asymmetrical pulses.
- Other features judged by the Investigator to be consistent with a GCA or PMR flare.

The resolution of signs and symptoms of GCA is identified in eCRF “GCA Assessment” page with the question “Based upon the patient’s relevant medical history and the clinical assessment and responses provided above, does the patient have active GCA?” ticked as “No”. The resolution of signs and symptoms of GCA by Week 12 will be determined based on the last non-missing post-baseline GCA assessment measured up to Week 12.

Patients who took rescue CS due to active GCA prior to Week 12 or who permanently withdraw from the study treatment prior to Week 12 will be considered as not achieved disease remission by Week 12.

2. Absence of disease flare from Week 12 through Week 52.

Flare is defined as either 1) recurrence of signs and symptoms attributable to active GCA plus an increase in CS dose due to GCA, or 2) elevation of ESR attributable to active GCA plus an increase in CS dose due to GCA. Increase in CS dose is defined as:

- Any dose increase during the protocol defined steroid taper, or
- Reinitiation of prednisone therapy after the protocol defined taper has been completed.

Patients with disease flare are identified as those with the reason for treatment ticked “rescue therapy” in eCRF “Steroid Medication” page and to the question “If Rescue Therapy, please specify” ticked either “Active GCA” or “Elevated ESR Attributable to Active GCA”.

3. Normalization of CRP (to <10 mg/L, with an absence of successive elevations to ≥10 mg/L) from Week 12 through Week 52

The status of normalization of CRP from Week 12 through Week 52 will be determined based on the CRP values measured at Week 16, Week 20, Week 24, Week 32, Week 40 and Week 52. If there are two or more consecutive visits with CRP ≥10 mg/L, then it is categorized as no normalization of CRP. Intermittent missing CRP at Week 16, Week 20, Week 24, Week 32, Week 40 or Week 52 will be imputed using last value carried forward (LOCF) approach.

4. Successful adherence to the prednisone taper from Week 12 through Week 52

Successful adherence to the prednisone taper from Week 12 through Week 52 is defined as patients did not take rescue therapy from Week 12 through Week 52 and may include the use of any excess prednisone (beyond the per protocol CS tapering regimen) with a cumulative dose of ≤100 mg (or equivalent), such as those employed to manage AE not related to GCA. The cumulative dose of excess prednisone use will be counted from baseline to Week 52.

In addition, patients who permanently withdraw from the study treatment prior to Week 52 will be considered as not achieved component 2, 3, or 4 for the primary endpoint.

Additional Endpoint: Sustained remission at Week 24

Based on patients’ enrollment dates and the study discontinuation plan, all patients would have had the opportunity to be treated for at least 24 weeks. As a result, an additional endpoint, sustained remission at Week 24, which is defined similarly as the primary endpoint but with shorter sustained period, is added in the SAP.

The sustained remission at Week 24 is defined by having met all of the following parameters:

- Achievement of disease remission not later than Week 12,
- Absence of disease flare from Week 12 through Week 24,
- Normalization of CRP (to <10 mg/L, with an absence of successive elevations to ≥10 mg/L) from Week 12 through Week 24, and
- Successful adherence to the prednisone taper from Week 12 through Week 24.

Components of the sustained remission at Week 24 are described as below:

- 1. Achievement of disease remission not later than Week 12**, which is defined in the same way as described for the primary endpoint.
- 2. Absence of disease flare from Week 12 through Week 24**, where disease flare is defined in the same way as described for the primary endpoint.
- 3. Normalization of CRP (to <10 mg/L, with an absence of successive elevations to ≥10 mg/L) from Week 12 through Week 24**

The status of normalization of CRP from Week 12 through Week 24 will be determined based on the CRP values measured at Week 16, Week 20, Week 24. If there are two or more consecutive visits with CRP ≥10 mg/L, then it's categorized as no normalization of CRP. Intermittent missing CRP at Week 16, Week 20 or Week 24 will be imputed using last value carried forward (LOCF) approach.

4. Successful adherence to the prednisone taper from Week 12 through Week 24

Successful adherence to the prednisone taper from Week 12 through Week 24 is defined as patients did not take rescue therapy from Week 12 through Week 24 and may include the use of any excess prednisone (beyond the per protocol CS tapering regimen) with a cumulative dose of ≤100 mg (or equivalent), such as those employed to manage AE not related to GCA. The cumulative dose of excess prednisone use will be counted from baseline to Week 24.

In addition, patients who permanently withdraw from the study treatment prior to Week 24 will be considered as not achieved component 2, 3, or 4 for the primary endpoint.

Blinding of CRP and ESR assessment results

Investigators, including Efficacy Assessors, and patients will remain blinded to CRP and ESR results (except screening and baseline). Safety Assessors will also be blinded on post baseline CRP but will have access to ESR results.

ESR kits will be provided by the central laboratory while the test will be performed locally at site, results (the distance in millimeters (mm) that red blood cells has descended in 1 hour) will be blinded to Investigators including Efficacy Assessors and staff directly involved in efficacy assessment of study patients.

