9 ASSESSMENT OF INVESTIGATIONAL MEDICINAL PRODUCT

9.1 PRIMARY ENDPOINT

9.1.1 Primary efficacy endpoint

Proportion of patients achieving sustained remission at Week 52. Sustained remission at Week 52 is defined by having met all of the following parameters:

- Achievement of disease remission not later than Week 12.
AND
- Absence of disease flare from Week 12 through Week 52.
AND
- Normalization of CRP (to <10 mg/L, with an absence of successive elevations to ≥ 10 mg/L) from Week 12 through Week 52, and
AND
- Successful adherence to the prednisone taper from Week 12 through Week 52.

Disease remission is defined as resolution of signs and symptoms of GCA, and normalization of CRP (<10 mg/L).

Note: A single CRP elevation (≥ 10 mg/L) is not considered absence of remission unless CRP remained elevated (≥ 10 mg/L) at the next study visit.

Signs and symptoms of disease

Evaluation of clinical signs and symptoms by the Efficacy Assessor at every study visit according to the schedule of assessment will include the following:

- Symptoms of PMR as indicated by the Efficacy Assessor (morning stiffness and/or pain, in the shoulder and/or hip girdles)
- Cranial symptoms.
 - Localized headache.
 - Temporal artery or scalp tenderness.
 - Visual signs or symptoms such as acute or subacute vision loss due to arteritic anterior ischemic optic neuropathy (A-AION), transient blurry vision (generally monocular or at least affecting 1 eye at a time, but potentially affecting both eyes), diplopia.
 - Jaw or mouth pain, tongue claudication.

- Constitutional syndrome, including but not limited to fever, malaise, unintentional weight loss, night sweat, asthenia, fatigue, loss of appetite.
- New or worsened extremity claudication, bruits and asymmetrical pulses.
- Other features judged by the Investigator to be consistent with a GCA or PMR flare.

Flare is defined as either 1) recurrence of signs and symptoms attributable to active GCA plus an increase in CS dose due to GCA, or 2) elevation of ESR attributable to active GCA plus an increase in CS dose due to GCA. Increase in CS dose is defined as:

- Any dose increase during the protocol defined steroid taper.
- Reinitiation of prednisone therapy after the protocol defined taper has been completed.

Blinding of CRP and ESR assessment results

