1.6 STATISTICAL MODIFICATIONS MADE IN THE STATISTICAL ANALYSIS PLAN

Due to the early termination of the study and study discontinuation plan, a large amount of data will not be able to be collected since many enrolled patients will not complete all planned study visits and study procedures for the assessments of efficacy, ADA, and biomarker endpoints. In addition, the number of randomized patients is 83 in 4 arms (out of 360 planned) at the time of the premature termination of the study. The changes from the statistical analysis plan outlined in the protocol are summarized below.

- The primary endpoint for the study is sustained remission at Week 52. Based on patients' enrollment dates and the study discontinuation plan, only about 36 patients (out of 83) had an opportunity to complete the 52-week treatment period. For the cohort of patients who

did not have an opportunity to complete the 52-week treatment period, it is not meaningful to define the endpoint of sustained remission at Week 52. Therefore, the analysis of primary endpoint will be limited to the cohort of patients who had an opportunity to complete the 52-week treatment period. Details can be found in [Section 2.1.3.1](#) and [Section 2.4.4.1](#).

- Based on patients' enrollment dates and the study discontinuation plan, all patients should have had the opportunity to be treated for at least 24 weeks, so an additional endpoint, sustained remission at Week 24, is added in the SAP. Details can be found in [Section 2.1.3.1](#).
- Due to the same reason as mentioned above, the secondary endpoints of cumulative GTI scores at Week 52 will be limited to the cohort of patients who had an opportunity to complete the 52-week treatment period. In addition, the cumulative GTI scores will also be assessed at Week 24. Details are provided in [Section 2.1.3.2](#).
- The missing data imputation strategy for defining the endpoints of sustained remission at W24 and W52, and cumulative GTI scores at W24 and W52 can be found in [Section 2.1.3.1](#) and [Section 2.1.3.2](#), respectively; the rest of efficacy analyses will be based on data as observed, no missing data will be imputed.

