- A statistically significance level of 0.01 (2-sided) was prespecified in the protocol for all the between group comparisons. Due to reason mentioned in the first bullet, the analysis of the primary endpoint of sustained remission at Week 52 will be limited to the cohort of patients who had an opportunity to complete the 52-week treatment period (n=36). With a total of 36 patients, the powers on the primary endpoint are minimal. Therefore, all the analyses will be descriptive in nature.
 - a) For majority of the efficacy endpoints, only descriptive summary statistics will be provided by 4 treatment groups.
 - b) For the primary and some selected important secondary endpoints, summary statistics and formal statistical tests on between group comparisons (with 95% CI and p-value) will be provided for the 2 combined treatment groups (ie, 2 sarilumab groups combined versus 2 placebo groups combined). Details are provided in [Section 2.4.4](#).
- No multiplicity/hierarchy testing will be applied; all p-values will be nominal.
- No subgroup analyses will be planned due to the small sample sizes.

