Appendix H Visit windows based on day ranges

Visit windows based on days relative to the first IMP dose will be used to map (see [Table 9](#)).

Table 9 - Day range for each scheduled visit in the DB period for efficacy, lab, vital sign, PK and ADA summaries

Visit Label	Target Day	Schedule A ^a	Schedule B ^b	Schedule C ^c	Schedule D ^d	Schedule E ^e	Schedule F ^f	Schedule G ^g	Schedule H ^h	Schedule I ⁱ	Schedule J ^j
Double-Blind Period											
Baseline	1	≤1	≤ 1	≤ 1	≤ 1	≤ 1		≤ 1	≤ 1	≤ 1	≤ 1
Week 2	15	>1'- 21							>1'-21	>1'-49	
Week 4	29	22-42				>1'-56	>1'-56	>1'-42	22 - 56		>1'-98
Week 8	57	43-70						43 - 70			
Week 12	85	71-98	>1'-126	>1'-126		57 - 126	57 - 126	71 - 98	57 - 98	50 - 126	
Week 16	113	99-126						99 - 126	99 - 140		
Week 20	141	127-154						127 - 154			
Week 24	169	155-196	127 - 224	127 - 266		127 - 224	127 - 224	155 - 196	141 - 266	127 - 266	≥ 99
Week 32	225	197-252						197 - 252			
Week 40	281	253-322	225 - 322			225 - 322	225 - 322	253 - 322			
Week 52	365	≥323	≥ 323	≥ 267	>1'	≥ 323	≥ 323	≥ 323	≥ 267	≥ 267	

a Includes temperature, heart rate, blood pressure, GCA clinical assessments (including disease flare), CRP, ESR

b Includes weight, glucocorticoid toxicity index (excluding bone density assessment)

c Includes physician global assessments (MD-VAS), patient reported outcomes and antibodies to sarilumab/ADA

d Includes bone density assessment, ANA

e Includes hematology: hemoglobin, hematocrit, red blood cell (RBC) count and morphology (if RBC count is abnormal), white blood cell (WBC) differential, platelet count, absolute neutrophil count (ANC) and chemistry: sodium, potassium, calcium, chloride, bicarbonate, total protein, creatinine and clearance, blood urea nitrogen (BUN), uric acid, lactate dehydrogenase (LDH), phosphate, albumin, ALT (SGPT), AST (SGOT), alkaline phosphatase (ALP), total bilirubin, conjugated bilirubin, and unconjugated bilirubin

f Includes HbA1c, fasting glucose, fasting lipids: triglycerides (TG), total cholesterol, HDL, LDL

g Includes urine pregnancy test

h Includes serum sarilumab

i Includes biomarkers-IL-6 and sIL-6R

j Includes immune cell phenotyping (whole blood)

* Includes value measured on day 1 but after the first IMP dose

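### SAP component 3 judges CRP from Week 12 but derives it from Week 16, so no rule tests a consecutive elevation at Weeks 12 and 16

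*SAP*

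**What the plan says.** Protocol 9.1.1 defines the CRP part of sustained remission over Week 12 through Week 52: values below 10 mg/L, without successive elevations to 10 mg/L or more. Its note adds that a single elevation "is not considered absence of remission unless CRP remained elevated" at the next study visit. SAP 2.1.3.1 repeats this definition.

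The SAP then gives derivation rules.

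- **Component 1 (remission by Week 12).** CRP status is "determined based on the last two non-missing post-baseline CRP values measured up to Week 12". One of the two below 10 mg/L is enough to pass.
- **Component 3, Week 52 endpoint.** "The status of normalization of CRP from Week 12 through Week 52 will be determined based on the CRP values measured at Week 16", followed by Weeks 20, 24, 32, 40 and 52. Two or more consecutive visits at 10 mg/L or more is a failure.
- **Component 3, added Week 24 endpoint.** "The status of normalization of CRP from Week 12 through Week 24 will be determined based on the CRP values measured at Week 16", followed by Weeks 20 and 24, with the same failure rule.
- **Missing values.** The last-value-carried-forward (LOCF) rule starts at the same visit: "Intermittent missing CRP at Week 16, Week 20, Week 24, Week 32" and the later visits. Week 12 is not in that list.

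CRP is scheduled at Week 12 in the study flow chart. In SAP Appendix H, Table 9, Schedule A ("Includes temperature, heart rate, blood pressure, GCA clinical assessments (including disease flare), CRP, ESR") gives it its own Week 12 window, days 71 to 98.

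**The concern.** The derivation sentence names a window starting at Week 12 but uses values starting at Week 16. For an elevated Week 12 value, the next study visit is Week 16, and neither component looks at those two values together. A patient whom the definition excludes can then be counted as a responder.

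This touches the Week 52 primary endpoint, the added Week 24 endpoint, and the stand-alone CRP component reported under SAP 2.1.3.2 and 2.4.4.2. Two programmers, one working from the definition and one from the visit list, could classify the same patient differently.

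**Working it through.** There is no figure in the plan to reproduce. The check is whether the derivation rules give the same answer as the definition.

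**Which pairs are tested (complete data)**

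| Adjacent CRP visits | Tested by |
|---|---|
| Weeks 8/12 | Component 1 (fails only if both are elevated) |
| Weeks 12/16 | No rule |
| Weeks 16/20, 20/24 and later pairs | Component 3 |

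**Counterexample (Week 24 endpoint).** CRP 5, 20, 20, 5, 5 mg/L at Weeks 8, 12, 16, 20, 24.

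- Component 1 uses Weeks 8 and 12 (5 and 20). One is below 10, so it passes.
- Component 3 uses Weeks 16, 20 and 24 (20, 5, 5). No two consecutive values are elevated, so it passes.
- Definition from Week 12: Weeks 12 and 16 are successive elevations, so the patient fails.

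No other component examines CRP.

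**Enumeration.** Code each visit as elevated or not and list every pattern. Apply the rules as written, then again with Week 12 at the head of the component 3 list. These are logical counts, not patient frequencies.

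| Case (complete data) | Patterns | Pass as written | Pass with Week 12 added | Pass only through the gap |
|---|---|---|---|---|
| Components 1 and 3, Weeks 8 to 24 | 2^5 = 32 | 15 | 13 | 2 |
| Components 1 and 3, Weeks 8 to 52 | 2^8 = 256 | 63 | 55 | 8 |
| Component 3 alone, Weeks 12 to 24 | 2^4 = 16 | 10 | 8 | 2 |
| Component 3 alone, Weeks 12 to 52 | 2^7 = 128 | 42 | 34 | 8 |

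In components 1 and 3 together, every pattern that passes only through the gap is normal at Week 8, elevated at Weeks 12 and 16, and normal at Week 20. The stand-alone component has no Week 8 condition.

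**With at most one missing value, Weeks 4 to 24.** There are 64 complete patterns and 6 × 32 = 192 with one value missing, 256 in all. As written, 115 pass. The result then depends on how the repair treats missing values:

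- Test Weeks 12/16 only when both are measured: 105 pass. The 10 that change all have measured elevations at both visits.
- Add Week 12 to the visit list and let a Week 12 value carried into a missing Week 16 count as a second elevation: 101 pass. The 4 further changes rest on one Week 12 value counted twice.
- Also impute a missing Week 12 from Week 8: 99 pass. The 2 further changes use a Week 8 value from before the window.

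**Size of one reclassified patient.** SAP Table 1 gives 42 combined sarilumab and 41 combined placebo patients, with assumed rates of 53% and 17%. The nearest whole counts are 22/42 and 7/41. One patient is 1/42 or 1/41, about 2.4 points either way. P-values are from a chi-square test without continuity correction or stratification; the SAP specifies a stratified CMH test, so they are illustrative.

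| Sarilumab | Placebo | Difference (points) | p |
|---|---|---|---|
| 22/42 | 7/41 | 35.3 | 0.0007 |
| 22/42 | 6/41 | 37.7 | 0.0003 |
| 21/42 | 7/41 | 32.9 | 0.0015 |

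The arm split of the 36 patients in the Week 52 Analysis set is not given. If 12 to 24 were on placebo (an assumption), one placebo patient would be 1/12 = 8.3 to 1/24 = 4.2 points.

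**The case against.** Week 12 is already used in component 1, so a non-overlapping start at Week 16 could be deliberate. The visit list is explicit and reproducible, and LOCF can bring Week 12 in. In part this is fair, but it does not close the gap. The SAP nowhere states a later start and still words the window from Week 12. LOCF uses the Week 12 value only when Week 16 is missing, so it never tests a measured pair.

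SAP 1.6 introduces its list with "The changes from the statistical analysis plan outlined in the protocol are summarized below" and does not mention a later start. A reader might infer an undisclosed change of endpoint. That goes too far: the protocol has no visit-by-visit CRP algorithm, and the list in 1.6 is framed around early termination. Silence there says little about an operational visit list.

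Two objections to a broader version of this point stand. Weeks 12/16 is not the only untested pair in the whole study: with complete data, Weeks 2/4 and 4/8 are not tested either, but they lie before the window. And a repair that extends LOCF to Week 12, or counts a carried-forward Week 12 value as a second elevation, goes beyond the stated definition. It would also sit badly with the protocol's note on single elevations.

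**Conclusion.** The definition and its derivation rule disagree, and the gap can only add responders. It is a minor point. The documents give no CRP frequencies, so the number of patients cannot be estimated; it is probably very small.

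A reader might take 2 of 15 or 8 of 63 as the share of responders affected. Those ratios weight every pattern equally and say nothing about patients.

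A reader might also infer that the gap favours sarilumab. The documents do not support that. SAP 2.4.4.1 refers to sarilumab's known effect on acute phase reactants, which makes paired elevations more plausible on placebo and would shrink the difference; that too is inference, so the direction of any bias between arms is not established.

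In the Week 24 illustration, one patient does not alter the reading of the result. SAP 1.6 states "No multiplicity/hierarchy testing will be applied; all p-values will be nominal", and the sensitivity analysis that removes CRP and ESR is unaffected.

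**What to change.** In component 3 of both endpoint definitions in SAP 2.1.3.1, and so in the stand-alone CRP component, start the visit list at Week 12. Keep the rule on two or more consecutive visits, and keep LOCF from Week 16 on as it is.

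Add two clarifications:

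- The Week 12/Week 16 comparison applies when both values are measured, so one elevated Week 12 value carried into a missing Week 16 is not by itself a failure.
- A missing Week 12 is not imputed from Week 8, which precedes the window.

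The cost is a short text edit and a small programming change; the data are already scheduled. A few responders with measured elevations at both visits may become nonresponders. A missing Week 16 is then handled slightly differently for this pair than missing values at later visits, and the SAP should say so.
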